1.4.2 AUXILLARY MEDICINAL PRODUCT: FOLIC ACID

Participants taking methotrexate will also take 5mg folic acid once weekly as per standard guidance for the prevention of side effects related to folate deficiency. The folic acid will be labelled with a standard dispensing label in accordance with Schedule 5 to The Medicines for Human Use (SI 1994/3194) (Marketing Authorisations etc) Regulations 1994 on receipt of a valid prescription. It will be stored in accordance with the storage conditions outlined on the commercial pack/relevant SmPC. Hospital stock will be used with no reimbursement from the sponsor. It must clearly documented in the medical notes and CRF when a prescription is issued.

1.4.3 SAFETY VISITS AND MONITORING REQUIREMENTS

Timing of post-randomisation safety tests (bloods, urine, blood pressure and safety assessment) are shown in the main protocol schedule of events (Table 1, section 2 Trial Design), and in the drug-

specific schedule of events at the beginning of each drug-specific appendix. Further details, including the exact laboratory tests required, are provided below.

1.4.3.1 SAFETY VISITS (IN ADDITION TO MAIN TRIAL VISITS)

All participants randomised to methotrexate will be followed up for safety at week 2. In addition, if their dose is increased at 3 months, they will be seen at weeks 15 and 17. At month 6, all patients who are switched to methotrexate will be followed for safety at weeks 28 and 30. In addition, if their dose is increased at month 9, they will be seen again at weeks 41 and 43. In the event of dose reduction, additional safety assessments should be arranged at the discretion of the investigator.

1.4.3.2 SAFETY BLOODS

The following safety bloods will be performed at weeks 2, 4, 13, 26, 39 and 52. For those who dose increment at month 3 additional safety bloods will be performed at weeks 15 and 17. For those who switch on to methotrexate at month 6 additional safety bloods will be performed at weeks 28 and 30. For those who increase dose at month 9, further saftey bloods will be performed at weeks 41 and 43.

HAEMATOLOGY Haemoglobin Haematocrit Total and differential leukocyte count Red blood cell count Platelet count

BIOCHEMISTRY Creatinine Potassium Liver function tests (LFTs)

1.4.3.3 URINE PREGNANCY TEST

A urine pregnancy test is required for those who switch on to methotrexate at the 6 month stage.

1.4.4 METHOTREXATE POLYGLUTAMATE LEVEL (MONTHS 1,3,6)

Methotrexate arm patients only, please refer to lab manual for full procedure on how to collect and send samples.

1.4.5 MANAGING TOXICITY WITH METHOTREXATE

Methotrexate is the most commonly prescribed standard systemic therapy for this study population (aduluts with moderate-severe eczema) in the UK, but is used off license. Investigators should refer to the relevant summary of product characteristics in the event of toxicity.

Further British Association of Dermatologists drug related guidance for the safe and effective prescribing of methotrexate can be found here:

Methotrexate: https://onlinelibrary.wiley.com/doi/epdf/10.1111/bjd.14816

1.4.6 EVALUATING AE'S AND SAE'S – ASSESSMENT OF EXPECTEDNESS

Section 4.8 of the following SmPC forms the RSI for methotrexate for this trial: Metoject PEN solution for injection pre-filled pen (dated 18/09/2024). This can be found in investigator site files (SmPC & Safety Alert Updates).

1.5 **REFERENCES**

- 5. Védie A-L, Ezzedine K, Amazan E, Boralevi F, Milpied B, Taïeb A, *et al.* Long-term Use of Systemic Treatments for Moderate-to-Severe Atopic Dermatitis in Adults: A Monocentric Retrospective Study. *Acta Dermato-Venereologica* 2016;96:802-6.

APPENDIX 3 DRUG-SPECIFIC INFORMATION: DUPILUMAB

TRIAL PARTICIPANT FLOW AND SCHEDULE OF EVENTS: DUPILUMAB

The electronic version of this document is the latest version. It is responsibility of the individual to ensure any paper material is the current version. Printed material is uncontrolled documentation. BEACON_PROTOCOL_VERSION 2.1_29.01.2025 clean.docxPage 90 of 110 Г

DUPIL	UMAB	SCHEDULE	OF EVENTS

Event / form	Screening	Baseline ^A	Week 4 (Month 1)	Week 13 (Month 3)	PRIMARY OUTCOME Week 26 (Month 6)	Week 30 safety visit	Week 39 (Month 9)	Week 52 (Month 12) End of Study Visit	Ongoing
Informed Consent	Х								
Registration Form	Х								
Eligibility (confirmation only at baseline)	Х	Х							
Medical History and demographics	Х								
Skin photography (optional)		Х			Х				
Randomisation Form (after all baseline data collected)		Х							
Status Form			Х	Х	Х		Х	Х	
Physical examination*	Х	Х	Х	Х	Х		Х	Х	
Blood pressure	Х	Х							
Urinalysis	Х								
Pregnancy test ⁺		Х							
Eczema Area and Severity Index (EASI) BLINDED ASSESSOR		x	х	х	х		х	х	
Investigator Global Assessment (vIGA-AD) BLINDED ASSESSOR		х	х	х	х		х	х	
Patient Orientated Eczema Measure (POEM)		Х	Х	Х	Х		Х	Х	
Peak pruritus numerical rating scale (NRS)		Х	Х	Х	Х		Х	Х	
Eczema control (RECAP)		Х	Х	Х	Х		Х	Х	
Patient global assessment (PtGA)		Х	Х	Х	Х		Х	Х	
Dermatology Life Quality Index (DLQI)		Х	Х	Х	Х		Х	Х	
EQ-5D-5L		Х		Х	Х		Х	Х	
PHQ-9		Х			Х			Х	
GAD-7		Х			Х			Х	
Resource use		X		Х	Х		Х	Х	
Adherence check (VAS) & Tolerability				Х	Х		Х	Х	
Participant Online Surveys		Х						Х	
Dispense medication		Х		Х	Х		Х		
Screening blood tests (+DNA for filaggrin status, optional)	х								
Safety Blood Tests (can be remote)		Х		Х	Х		X++	Х	
Safety assessment (can be remote)**						Χ			
Study medication switch review					Х				
Study medication dose increment review				Х			X		
Concomitant Medications Log									Х
Topical treatments		Х	Х	Х	Х				
Adverse Events Log									X
Withdrawal Form									X
* Physical examination (according to routine clinical care) require	ed at sci	reening	and bas	seline,	extent of	physica	al exam d	uring follo	w

eemed appropriate by investigat

** Only for those who switched treatment to dupilumab at 6 months

+ Women of childbearing potential only. Urine test

++ Not required for those on dupilumab from the start (week 39 blood tests required for those who switch to dupilumab)

A: Baseline safety bloods for all treatments, at investigator discretion based upon timing of screening bloods

Please note: if IMP is switched at 6 months, the schedule of events for the second IMP must be followed for the second 6 months of the trial.

CONTENTS

1	DUPI	LUMAB-SPECIFIC INFORMATION	93
	1.1	BACKGROUND	93
	1.1.1	Background and mechanism	93
	1.1.2	Rationale for use of dupilumab	93
	1.1.3	Dupilumab dose justification	93
	1.1.4	Rationale for 6 month switch option for those who fail to respond to dupilumab (methotrexate)	93
	1.2	DUPILUMAB TOXICITY AND SAFETY	93
	1.2.1	Common side effects	93
	1.2	.1.1 Ocular reactions	93
	1.2.2	Uncommon side effects	94
	1.2.3	Rare side effects	94
	1.2.4	Drug interactions	94
	1.3	SELECTION OF PARTICIPANTS	94
	1.3.1	Participant core inclusion and exclusion criteria	94
	1.3.2	Dupilumab-specific exclusion criteria	94
	1.4	TREATMENT AND MONITORING OF PARTICIPANTS: DUPILUMAB	94
	1.4.1	Product information	94
	1.4.2	Safety visits and monitoring requirements	95
	1.4	.2.1 Safety visits (in addition to main trial visits)	96
	1.4	2.2.2 Safety bloods	96
	1.4.3	Managing toxicity with Dupilumab	96
	1.4.4	Evaluating AE's and SAE's – assessment of expectedness	96
	1.5	REFERENCES	96

1 DUPILUMAB-SPECIFIC INFORMATION

1.1 BACKGROUND

1.1.1 BACKGROUND AND MECHANISM

Dupilumab is a fully human IgG monoclonal antibody that binds with specificity to the shared IL-4 receptor alpha subunit of the IL-4 and IL-13 cytokine receptors. By binding to that subunit, dupilumab inhibits IL-4 signaling through the Type I receptor (IL-4Ra/yc) and IL-4 and IL-13 signaling through the Type II receptor (IL4Ra/IL-13Ra). IL-4 and IL-13 are major drivers of human type 2 inflammatory disease including atopic eczema and asthma. IL-4 induces differentiation of naïve helper T-cells to Th2 cells which in turn produce further IL-4 to create a positive feedback loop. Th2 cells produce IL-13 which is a mediator of allergic inflammation affecting the skin barrier, pathogen defense, fibrosis and neuronal sensitization within the skin^{1,2}.

1.1.2 RATIONALE FOR USE OF DUPILUMAB

Dupilumab is a comparator as it is a widely adopted (most commonly prescribed 'novel' treatment), new, licensed, effective and targeted therapy, but has high costs, consequent NICE-defined access criteria and there is genuine clinical equipoise with the existing treatments (see section 1.1.1 and 1.4 in main protocol for further background information).

1.1.3 DUPILUMAB DOSE JUSTIFICATION

Dupilumab has one standard licensed dose for the treatment of adults with moderate to severe eczema, which has been utilised in this trial.

1.1.4 RATIONALE FOR 6 MONTH SWITCH OPTION FOR THOSE WHO FAIL TO RESPOND TO DUPILUMAB (METHOTREXATE)

For those participants on dupilumab who do not meet response criteria to continue at 6 months they can switch to methotrexate. Methotrexate was chosen because it represents the most commonly prescribed first line systemic treatment for atopic eczema in the UK, it can be safely continued beyond 12 months (unlike ciclosporin), there would be no funding issue preventing continuation post-trial and it has a more contrasting mechanism of action compared to other novel agents (e.g. JAKi). This will also provide novel information on the sequential benefit of switching from dupilumab to methotrexate and would mean that participants would be eligible to move on to a more novel agent post-trial (e.g. JAKi) if needed.

1.2 DUPILUMAB TOXICITY AND SAFETY

Administration of dupilumab for this study is not anticipated to induce any potential risk other than the known potential side effects listed below (see SmPC).

1.2.1 COMMON SIDE EFFECTS

Conjunctivitis; allergic conjunctivitis; arthralgia; eosinophilia; oral herpes; injection site reactions (including erythema, oedema, pruritis, pain, swelling, and bruising).

1.2.1.1 OCULAR REACTIONS

Dupilumab is commonly associated with cases of conjunctivitis and allergic conjunctivitis, eye pruritus, blepharitis, and dry eye and with infrequent cases of keratitis and ulcerative keratitis. In line with MHRA drug safety update (November 2022), clinicians are advised to be alert to the risks of

ocular reactions and promptly review new onset or worsening ocular symptoms, referring patients for ophthalmological examination as appropriate. Conjunctivitis or dry eye that does not resolve following initial treatment, or patients with signs and symptoms suggestive of keratitis (especially eye pain and vision changes) should undergo ophthalmological examination, as appropriate. Sudden changes in vision and significant eye pain warrant urgent ophthalmology review.

Clinicians should discuss with patients or caregivers the potential for, and symptoms of, ocular side effects at initiation of dupilumab, including symptoms of conjunctivitis and dry eye (which can also include paradoxical eye watering), keratitis and ulcerative keratitis and advise patients to promptly report new-onset or worsening eye symptoms to their healthcare professional so that appropriate treatment can be initiated.

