3.2 SECONDARY OBJECTIVES

- 1. Determine the effectiveness of systemic treatments compared with standard of care over 12 months
- 2. Determine the impact on symptoms, quality of life, daily function and mood of systemic treatments compared with standard of care over 12 months
- 3. Determine the safety / tolerability of systemic treatments compared with standard of care, and adherence to the medications over 12 months
- 4. Determine cost-effectiveness of systemic treatments compared with standard of care over 12 months
- 5. Collect data on which first line therapy optimises treatment continuity over the first year and in the event of a treatment switch, which of the tested pathways optimises treatment outcomes at one year.
- 6. Determine the incidence of AEs of special interest (see section 10.2 for further information) on systemic treatments compared with standard of care over 12 months
- 7. Collect clinical data and samples for use by the scientific community to understand atopic eczema disease biology and treatment response in order to improve outcomes in people with atopic eczema.

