6.5.3 ADVERSE EVENTS

During each visit, participants will be asked about adverse events (see section 10). All adverse events will be recorded in an ongoing adverse event log stating start/ end date, severity, serious adverse event, relatedness to study medication, relatedness to study procedure, impact on treatment and outcome. Adverse events of special interest will be captured in more detail (see section 10.2).

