10.2 ADVERSE EVENTS OF SPECIAL INTEREST (AESI)

The AESI listed below will be recorded in more detail via AESI report forms throughout the trial. A template document outlining the information to be recorded will be provided to sites, to be recorded onto Source Data Worksheets or directly into the participants medical records for transcribing into the MACRO eCRF system:

- Ocular surface disease e.g. conjunctivitis/ blepharitis/ keratitis/ dry eye/ keratoconus
- Pain in or around joints
- Facial skin rashes (including acne)

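### Ocular AESIs may be over-ascertained on dupilumab relative to the other arms, because eye-symptom counselling and referral triggers appear only in the dupilumab appendix

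*Protocol*

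**What the plan says.** Protocol Appendix 3, section 1.2.1.1 (Ocular reactions), rests on a regulator's safety notice: "In line with MHRA drug safety update (November 2022), clinicians are advised to be alert to the risks of" ocular reactions. Clinicians are to discuss "ocular side effects at initiation of dupilumab" and "advise patients to promptly report new-onset or worsening eye symptoms to their healthcare professional". It sets out when ophthalmological examination is wanted (conjunctivitis or dry eye that does not settle after initial treatment, or suspected keratitis) and adds: "Sudden changes in vision and significant eye pain warrant urgent ophthalmology review".

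Appendices 1 (ciclosporin), 2 (methotrexate) and 4 (abrocitinib) have no ocular section, although Appendix 2 lists conjunctivitis as a rare side effect and Appendix 4 lists ophthalmic herpes as a common one.

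Section 10.2 makes "Ocular surface disease e.g. conjunctivitis/ blepharitis/ keratitis/ dry eye/ keratoconus" the first AESI, with no restriction by arm, and says "The AESI listed below will be recorded in more detail via AESI report forms throughout the trial". Section 3.2, objective 6, is to "Determine the incidence of AEs of special interest" on systemic treatments against standard of care over 12 months. Section 6.5.3 gives the common route by which events come to light: "During each visit, participants will be asked about adverse events (see section 10").

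Table 2 (section 8.4) lists participants, treating clinicians and local research teams as unblinded. Only the EASI and IGA assessors at site are blinded.

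**The concern.** Participants who start dupilumab are told what eye symptoms to look for and to report them promptly, and persistent symptoms lead to a specialist examination that may supply a diagnosis. For the other arms the protocol describes only the general question. Section 1.1 names allergic conjunctivitis among the common co-morbidities of eczema, so some eye symptoms can be expected in every arm, and whether they are counted depends partly on how readily they are mentioned and recorded.

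Head-to-head safety data are part of the trial's rationale (section 1.1.1), and ocular surface disease is one of three AESIs chosen for closer study. If eye events are found more completely in one arm, the estimated excess over ciclosporin mixes drug effect with detection. No later analysis can recover symptoms that were never asked about, so the remedy belongs in data collection.

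**Working it through.** **Elicitation, arm by arm**

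| | Dupilumab | Ciclosporin, methotrexate, abrocitinib |
|---|---|---|
| Eye-symptom counselling at start | Yes (App. 3, 1.2.1.1) | None stated in Apps 1, 2, 4 |
| Advice to report eye symptoms promptly | Yes | None stated |
| Ophthalmology examination triggers | Yes | None stated |
| General AE question at each visit | Yes (6.5.3) | Yes |
| AESI report form | Yes (10.2) | Yes |
| Eye history and eye signs before randomisation | Yes (6.3.3, 6.3.5) | Yes |
| Scheduled eye item in follow-up | None in Table 1 | None in Table 1 |

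The extent of follow-up physical examination is left to the physician (section 6.5.1), so that does not equalise eye checks either.

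**Scheduled contacts to month 6**

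- Dupilumab: weeks 4, 13, 26 = 3 (App. 3, schedule and 1.4.2.1).
- Ciclosporin: weeks 2, 4, 6, 8, 13, 26 = 6, or 8 with weeks 15 and 17 after a dose increase (App. 1, schedule and 1.4.2.1).

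This difference favours detection on ciclosporin.

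**Illustration of size**

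The protocol gives no ocular incidence and no capture probability, so there is no figure of its own to reproduce. From the protocol: 134 per arm (12.1) and two-sided 0.025 (12.5.1, with 97.5% intervals for binary outcomes in 12.5.2). No test is stated specifically for AESI incidence, so 0.025 is carried over for illustration. Assumed: the same true incidence p in both arms, capture of 0.90 on dupilumab, and lower capture on ciclosporin.

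Observed incidence = p × capture, so the ratio due to ascertainment alone = 0.90 / capture on ciclosporin, whatever p is:

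- 0.90/0.80 = 1.125
- 0.90/0.60 = 1.50
- 0.90/0.45 = 2.00
- equal capture, 0.90/0.90 = 1.00

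Chance of a false excess on dupilumab, using the normal test of two proportions with n = 134 per arm and z = 2.2414:

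probability = Φ{(d − z × SE0) / SE1}, where d is the difference in observed proportions, SE0 the pooled standard error and SE1 the unpooled one.

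*p = 0.15, capture 0.90 v 0.60.* Proportions 0.135 v 0.090; expected counts 134 × 0.135 = 18.1 v 134 × 0.090 = 12.1. d = 0.045, SE0 = 0.0386, SE1 = 0.0385. Probability = 0.140.

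*p = 0.30, same capture.* Proportions 0.270 v 0.180; expected counts 36.2 v 24.1. d = 0.090, SE0 = 0.0510, SE1 = 0.0507. Probability = 0.316.

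*p = 0.10, same capture.* Proportions 0.090 v 0.060. Probability = 0.095.

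With equal capture the probability in that direction is 0.0125.

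**The case against.** A reader might infer that ocular incidence on dupilumab *is* inflated. The documents do not support that. Section 1.1.1 and Appendix 3 present ocular surface disease as a known dupilumab effect, so an excess may be real, and nothing in the protocol allows the bias to be measured.

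Further points on the other side:

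- **Shared ascertainment.** Every arm gets the visit question, the same AESI list and the same report form. The site template for AESIs is not shown and may already carry specific prompts. This limits the claim to what the protocol itself requires.
- **Other arms are counselled too.** Section 7.2 has the research team counsel every participant on the new medication, and side effects are in the information sheet (7.1), which is not shown. So it cannot be said that other participants hear nothing about eyes, only that the protocol's explicit eye instructions attach to dupilumab.
- **More contacts on ciclosporin.** This may offset part of the effect. The offset is uncertain: section 2 lets safety-only visits take place in general practice and asks for minimal contact with study staff.
- **Switching.** Ciclosporin and methotrexate non-responders can start dupilumab at month 6, and the counselling then applies to them. One might read this as adding to the inflation. Because section 12.3 analyses participants as randomised, their prompted reports count in their original arms and dilute the 12-month contrast instead.
- **The quoted text is not an error.** It is a regulator-derived safety measure in a pragmatic trial. This stands, and the fix does not touch it.
- **Scripted questions do not remove open-label bias.** Participants who know they are on dupilumab may still answer yes more readily. This also stands, and it is why the comparison should not rest on solicited symptoms alone.

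**Conclusion.** The concern holds as a risk of differential ascertainment, most plausibly towards more recorded ocular events on dupilumab. The asymmetry in the protocol's instructions is plain, the comparison is a stated secondary objective, and those who report and record the events are unblinded.

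The size is unknown. Under the assumed capture rates the spurious ratio runs from 1.1 to 2.0, and with 90% against 60% capture the chance of a false excess at two-sided 0.025 is about 14% at 15% true incidence and 32% at 30%. These rest wholly on assumed incidence and capture and on 134 assessed per arm; at 10% incidence the figure is about 9.5%. Extra contacts on ciclosporin and switching after month 6 work in the opposite direction by an amount the protocol does not allow one to calculate. The primary outcome is not affected. This is a cheap improvement to a secondary safety comparison.

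**What to change.** Leave the dupilumab safety advice in Appendix 3 unchanged.

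1. In sections 6.5.3 and 10.2, require the same scripted yes/no questions in every arm on the three AESI areas: eye symptoms, pain in or around joints, and facial rash. At baseline ask about current symptoms; at months 1, 3, 6, 9 and 12 ask about anything new or worse since the last visit.
2. For objective 6, report AESI incidence as defined in section 10.2 side by side with the incidence of solicited symptoms. Flag events that came to light only through a between-visit report or an ophthalmology referral.
3. Present both to month 6, before any protocol switch, as well as to month 12.
4. State in the report that some reporting bias from open-label treatment remains.

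Cost: one short eCRF item at visits already held in all arms. More mild AESIs will be recorded in every arm.

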1.2.2 UNCOMMON SIDE EFFECTS

Facial rash; keratitis; blepharitis; eye pruritis; dry eye; angioedema.

1.2.3 RARE SIDE EFFECTS

Ulcerative keratitis; anaphylactic reaction; serum sickness reaction; serum sickness-like reaction.

1.2.4 DRUG INTERACTIONS

Investigators should check for any relevant drug interactions in the dupilumab SmPC.

1.3 SELECTION OF PARTICIPANTS

1.3.1 PARTICIPANT CORE INCLUSION AND EXCLUSION CRITERIA

To be eligible for randomisation, all participants must fulfil the core inclusion criteria and none of the exclusion criteria stated in section 5.3 of the main protocol in addition to the arm-specific criteria below.

Please note, as long as a participant is eligible to take ciclosporin (control arm) and at least one of the other trial treatments they can be randomised (i.e. they can meet exclusion criteria for one or more of the other treatments and still be randomised). If they fail to respond at 6 months, a pre-defined treatment switch (as per protocol) may or may not be possible depending on whether they still meet exclusion criteria for the relevant switch option. If the switch is not possible, they would be withdrawn from the trial at that stage.

1.3.2 DUPILUMAB-SPECIFIC EXCLUSION CRITERIA

In addition to the core inclusion and exclusion criteria documented in the main protocol, the following arm-specific exclusion criteria apply for the dupilumab arm.

1. Any contraindication to dupilumab according to standard clinical care and/or the opinion of the investigator.

Please note: in relation to main exclusion criteria point 2 (main protocol section 5.3), systemic therapies in the same class as dupilumab would, for example, include tralokinumab and lebrikizumab.

1.4 TREATMENT AND MONITORING OF PARTICIPANTS: DUPILUMAB

1.4.1 **PRODUCT INFORMATION**

Dose: Self-administered sub-cutaneous injection, 600mg (week 0) followed by 300mg every 2 weeks. A dose reduction is permitted at any point and will be documented in the participants medical notes/Source Data Worksheets and CRF.

Description of product: Dupixent® 300 mg/2ml solution for injection in a pre-filled pen (if pen formulation unavailable/ inappropriate for any reason, syringe can be used). Patients/carers must receive training on administration for the formulation prescribed in accordance with the package leaflet.

Packaging: Commercial/licenced packaging.

Prescription: Trial-specific prescription. Prescription template to be provided by sponsor.

Source of product: Supplies are ordered by the site pharmacy procurement team. Reimbursement of the excess treatment costs will be managed locally by site staff.

Storage: Store in a refrigerator (2°C - 8°C). Do not freeze. Store in the original carton to protect from light.

Note: the pre-filled pens/syringes may be kept at room temperature up to 25°C for a maximum of 14 days. Do not store above 25°C. After removal from the refrigerator, Dupixent® must be used within 14 days or discarded. The trial supplies must be stored in a designated section of the fridge, which is clearly labelled and is in a separate location to the storage of hospital dupilumab supplies. In the event of a temperature excursion, manage according to local pharmacy practice.

Special precautions for handling: The solution should be clear to slightly opalescent, colourless to pale yellow. If the solution is cloudy, discoloured or contains visible particulate matter, the solution should not be used. After removing the 300 mg pre-filled pen/syringe from the refrigerator, it should be allowed to reach room temperature up to 25°C by waiting for 45 min before injecting. The pre-filled pen/syringe should not be exposed to heat or direct sunlight. Do not shake the pre-filled pens or syringes.

Labelling: Attach a dispensing label in addition to a Sponsor label. Refer to the pharmacy manual for further details.

Accountability: The pharmacy clinical trials team must maintain accurate accountability records for the formulation, including, but not limited to, the number of packs received, the number of packs dispensed to which participant, the number of unused packs in quarantine or destroyed, as well as a record of the batch number and expiry date. It must be clearly documented in the medical notes and CRF when a prescription is issued. There will be no patient diaries, consistent with the pragmatic trial design and real world practice. Adherence should be discussed at each trial visit. A record of study drug returns is not required for the trial. Any unused medicinal product or waste material should be disposed of in accordance with local requirements or by the participant within a sharps bin provided as per routine clinical practice. After use, place the pre-filled pen/ syringe into a puncture-resistant container and discard as required by local regulations.

